5.3. Summary of safety data

All enrolled patients will be included in the safety analysis. Details for analysis of AEs and hypersensitivity already reported in 5.1.1.

5.3.1. Safety blood test

In addition, results of blood tests at screening, weeks 4, 9, 14 & 20 will be reviewed to identify any abnormalities in the full blood count; urea, electrolytes and creatinine; liver function tests; (prothrombin time, total bilirubin, total protein, albumin, AST (SGOT), SGPT (ALT), alkaline phosphatase; thyroid stimulating hormone; immunoglobulins (G, A, M); calcium; magnesium, phosphate, lipid profile (total cholesterol, LDL, HDL, triglyceride). Types and frequency of abnormal blood test results per patient over time will be enumerated.

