17 days. Because the kidney was the most exposed vital organ in the animals used for the pre-clinical safety studies, a number of markers of kidney function will be monitored in the patients. Electrolytes, urea, creatinine, calcium, phosphate, and magnesium levels will be tested in blood. Urinalysis for blood, protein (cystatin-c) and beta-2-microglobulin will be performed in addition. A final analysis will be performed 12 weeks after the last dosing. There will also be an optional analysis at 12 months/ 52 weeks post last dose. For safety reasons, there will be an optional contact hypersensitivity/ skin testing to be performed anytime post final dose.

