5.3.3 Gold concentration

At visits 1, 1b, 3b, 4, 5 and 6 blood and urine samples will be taken for gold concentrations to enable assessment of gold excretion. Laboratory measurements for these will be performed at the LGC laboratory, Cambridgeshire. Concentration of gold for each patient over time will be analysed by half-life of elimination at the end of the study.

The major organ of accumulation and excretion of the gold nanoparticles is the kidney. Safety reports on markers of kidney function in blood (levels of electrolytes, urea, creatinine, calcium, phosphate, and magnesium) and urine (blood in urine, protein in urine, cystatin-c and beta-2-microglobulin) have already been covered in 5.3.1 and 5.3.2.

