|--------------|-----------|-------|-------|------------|----------|-----------------------|---------------------------|
| Screening No | Centre No | Rx No | AE no | Start date | End date | Serious? 1=Y / 2=N | If Y, print full SAE form |
|--------------|-----------|-------|-------|------------|----------|-----------------------|---------------------------|

Cont'd

| | | | |
|---|--|---|---|
| Severity 0=no AE, 1=mild, 2=moderate,3=severe | Study drug action 0=none 1=temp interrupt 2=permanently withdraw | Outcome 0=resolved 1=resolved with sequela 2=not resolved | Relationship to study drug 0=not related 1=unlikely 2=possibly 3=probably 4=very likely |
|---|--|---|---|

Table 9 shows the headings of the data file for safety blood test reporting

| | | | | | | |
|--------------|-----------|----------|-------------------------|---------------------------|------------------|------------------|
| Screening No | Centre No | Visit No | Hb (Males) Normal (Y/N) | Hb (Females) Normal (Y/N) | Hct Normal (Y/N) | MCV Normal (Y/N) |
|--------------|-----------|----------|-------------------------|---------------------------|------------------|------------------|

Cont'd

| | | | | | | |
|------------------|------------------|------------------|------------------------|--------------------------|------------------------|--------------------------|
| MCH Normal (Y/N) | WBC Normal (Y/N) | RBC Normal (Y/N) | Platelets Normal (Y/N) | Neutrophils Normal (Y/N) | Basophils Normal (Y/N) | Eosinophils Normal (Y/N) |
|------------------|------------------|------------------|------------------------|--------------------------|------------------------|--------------------------|

Cont'd

| | | | | | | |
|-------------------------------|--------------------|----------------------|-------------------------|------------------------|-------------------|---------------------|
| Prothrombin Time Normal (Y/N) | HbA1c Normal (Y/N) | Glucose Normal (Y/N) | Creatinine Normal (Y/N) | Potassium Normal (Y/N) | Urea Normal (Y/N) | Sodium Normal (Y/N) |
|-------------------------------|--------------------|----------------------|-------------------------|------------------------|-------------------|---------------------|

Cont'd

| | | | | | | |
|----------------------|------------------------|------------------------|-----------------------------------|----------------------------|----------------------|------------------------------|

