| Calcium Normal (Y/N) | Phosphate Normal (Y/N) | Magnesium Normal (Y/N) | Alkaline Phosphatase Normal (Y/N) | Total Protein Normal (Y/N) | Albumin Normal (Y/N) | Total Bilirubin Normal (Y/N) |
|----------------------|------------------------|------------------------|-----------------------------------|----------------------------|----------------------|------------------------------|

Cont'd

| | | | | | | |
|-------------------------|-------------------------|------------------|--------------------------------|-------------------|-------------------|----------------------------|
| AST (SGOT) Normal (Y/N) | ALT (SGPT) Normal (Y/N) | TSH Normal (Y/N) | Total Cholesterol Normal (Y/N) | HDLC Normal (Y/N) | LDLC Normal (Y/N) | Triglycerides Normal (Y/N) |
|-------------------------|-------------------------|------------------|--------------------------------|-------------------|-------------------|----------------------------|

Cont'd

| | | |
|------------------|------------------|------------------|
| IgA Normal (Y/N) | IgM Normal (Y/N) | IgG Normal (Y/N) |
|------------------|------------------|------------------|

List details as captured in CRF for parameter not within the normal range for the patient, visit and parameter concerned

Table 10 shows the headings of the data file for safety urine test reporting

| | | | | | |
|--------------|-----------|----------|------------------------|-----------------------|-----------------------------|
| Screening No | Centre No | Visit No | PH Blood Normal (Y/N)* | Protein Normal (Y/N)* | Pregnancy test (+ve, -ve)** |
|--------------|-----------|----------|------------------------|-----------------------|-----------------------------|

* List details as captured in CRF for parameter not within the normal range for the patient, visit and parameter concerned

**Please flag patients with positive pregnancy test

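### Blood kidney markers are summarised only as normal or abnormal, and cystatin C, beta-2-microglobulin and albumin/creatinine ratio have no stated summary, so a within-range renal shift would not appear in the planned safety analysis

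*SAP*

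**What the plan says.** SAP 5.3.1 reviews the safety bloods for abnormalities and gives one summary: "Types and frequency of abnormal blood test results per patient over time will be enumerated". In SAP Appendix 2, Table 9, each analyte is a single flag. The creatinine column begins "Creatinine Normal (Y/N", and urea, sodium, potassium, calcium, phosphate and magnesium are treated alike. Anything beyond the flag is requested only for abnormal results: "List details as captured in CRF for parameter not within the normal range for the patient, visit and parameter concerned".

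Protocol 10.1 explains why kidney markers are measured: "Because the kidney was the most exposed vital organ in the animals used for the pre-clinical safety studies". It reports that rat kidneys collected on average 30% of the administered dose. SAP 5.3.3 repeats that the kidney is the main organ of accumulation and excretion. It then says that the blood and urine kidney markers "have already been covered in 5.3.1 and 5.3.2".

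SAP 5.3.2 lists beta-2-microglobulin, albumin/creatinine ratio and cystatin C as collected. Its summary sentence covers only abnormal pH, blood and protein, plus positive pregnancy tests. SAP Table 10 has columns for those items only.

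The exclusion criteria in both documents bar patients with serum creatinine above the laboratory range.

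**The concern.** General safety is part of the primary objective, and the kidney is the organ that the preclinical work singled out. In a single group of 8 patients, within-patient change is the most informative use of the renal measurements. A normality flag cannot show change unless a limit is crossed. Patients enter with creatinine at or below the upper limit, so each has some room to rise without changing the flag.

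The urine side does not fill the gap. SAP 5.3.3 sends the reader to 5.3.2 for cystatin C and beta-2-microglobulin, but 5.3.2 describes only their collection. No kidney marker therefore has a stated analysis of its values. Elsewhere the SAP does plan within-patient differences: in 5.1.1 for autoantibodies and T cell responses, and in 5.1.2 for C-peptide and HbA1c.

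At stake is a final report that records no renal abnormalities when the measured values might show a common upward shift.

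**Working it through.** The plan gives no figure to reproduce. The sample size of 8 has no formula, and no power, alpha or standard deviation is stated for the safety bloods. The documents give no creatinine limits, so the ranges below are assumptions used only to show scale.

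**1. Room to rise within range.** For lower limit L and upper limit U, the largest rise that leaves the flag unchanged is U/L - 1. With 60-110 umol/L, a patient starting at 65, 80 or 100 can rise by 110/65 - 1 = 69%, 110/80 - 1 = 38% or 110/100 - 1 = 10%.

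**2. Share still at or below U after a rise r.** Take a normal reference population with 95% of values between L and U, so m = (L+U)/2 and s = (U-L)/(2 x 1.96). The share is Φ((U/(1+r) - m)/s).

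| Assumed range (umol/L) | U/L - 1 | r = 20% | r = 30% | r = 50% |
|---|---|---|---|---|
| 60-110 | 83% | 0.699 | 0.488 | 0.180 |
| 64-104 | 62.5% | 0.603 | 0.348 | 0.075 |
| 45-84 | 87% | 0.710 | 0.505 | 0.196 |

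The population includes the 2.5% who start above U and would be excluded at entry. Removing them divides each share by 0.975, for example 0.488/0.975 = 0.501.

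**3. What the flags show if all 8 patients rise.** The expected number flagged is 8 x (1 - share).
- At r = 20%: 8 x (1 - 0.710) = 2.3 to 8 x (1 - 0.603) = 3.2.
- At r = 30%: 8 x (1 - 0.505) = 4.0 to 8 x (1 - 0.348) = 5.2.
- The chance of no flag at all at r = 20% is 0.603^8 = 0.02 to 0.710^8 = 0.06.

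The flags therefore understate a large common shift rather than always missing it. They miss entirely any set of rises that stays within range.

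**4. What the values would show.** If all 8 patients rose, a change listing would show 8 of 8. The chance of that is (1/2)^8 = 1/256 if direction were random. For the mean percentage change, the 95% confidence interval half-width is t(7) x CV x √2/√8. With t(7) = 2.365 and an assumed within-patient CV of 4%, 5% or 10%, it is 4.7, 5.9 or 11.8 percentage points.

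**5. Is there a baseline?** Table 1 in both documents marks a safety blood at visit 1. SAP 5.3.1 and Protocol 10.1 list screening and weeks 4, 9, 14 and 20, without week 0. Protocol Figure 3 shows none at visit 1, and its visit 1 total agrees: 10 + 25 + 1 + 64 + 2 = 102. Without a visit 1 sample, the last pre-dose value is the screening value, which may be up to 3 months old.

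**6. Cystatin C.** Table 1 in both documents lists it as a serum test. Protocol 10.1 and SAP 5.3.2 describe a urine collection.

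**The case against.** The strongest reply is that the values are not lost. Clinicians review safety bloods at follow-up visits (Protocol 6.6), and the DSMB receives safety reports (SAP 5.3.2). SAP section 4 promises descriptive statistics, and Protocol 15.1 means, standard deviations and ranges. SAP Table 6 is a by-visit file for each analyte, and its full list sits in a Data Management Plan that is not among the documents. Numeric creatinine there can be neither confirmed nor excluded.

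This stands against any claim that a rise would go unnoticed by everyone. It does not supply a planned analysis. The general wording is not tied to the safety bloods, means cannot be computed from Table 9 flags, and 5.3.3 points only to 5.3.1 and 5.3.2.

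A second reply is that results already abnormal before dosing can be recognised, because the enumeration is per patient over time and starts at screening. With 8 patients that is fair. A treatment-emergent label adds clarity rather than recovering lost information.

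A reader might also infer that HbA1c and glucose flags, common in type 1 diabetes, would swamp the abnormal counts and hide new findings. The documents do not support this. Both tests are columns in Table 9 but absent from the 5.3.1 list. The enumeration is by type and per patient, so a glycaemic flag cannot mask a creatinine flag. HbA1c is also analysed as a change from baseline in 5.1.2. What remains is a small mismatch between Table 9 and 5.3.1.

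**Conclusion.** The point holds for the planned analysis. The SAP specifies no numeric summary or change from baseline for any kidney marker, and gives no summary at all for cystatin C, beta-2-microglobulin or albumin/creatinine ratio. A rise that stays within range in all 8 patients would give zero abnormal results. On the assumed 60-110 umol/L range, that allows a 38% rise from a start of 80, but only 10% from 100.

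A reader might go further and infer that any marked renal effect would be invisible. That is not supported. If all patients rose by 20% from starting values spread like a reference population, about 2 or 3 of the 8 would be flagged. The loss is of the within-patient pattern, not of every signal. These sizes rest on assumed reference limits and a normal spread of starting values. The gap itself follows from the SAP text alone. It is worth correcting because the correction is cheap and concerns the organ that the plan itself singles out.

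**What to change.** Amend SAP 5.3.1, 5.3.2 and Tables 9 and 10 as follows.

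- Transfer the numeric value and reference range for each result, alongside the existing flag. Add cystatin C, beta-2-microglobulin and albumin/creatinine ratio to the file.
- For creatinine, urea, electrolytes, calcium, phosphate, magnesium, cystatin C, beta-2-microglobulin and albumin/creatinine ratio, list each patient's value by visit. Show the absolute and percentage change from the last pre-dose value, with the group median and range.
- Mark an abnormality as treatment-emergent only if that result was within range before dose 1. The change listing will show any worsening of a result that was already abnormal.
- Reconcile whether a visit 1 safety blood is drawn, so that the baseline is defined, and whether cystatin C is a serum or urine test.
- Align Table 9 with the 5.3.1 list on HbA1c and glucose.

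The cost is a fuller laboratory file and a little more programming. The analysis uses tests already in the schedule and needs no additional sampling. SAP section 8 already provides the amendment route through the DSMB.

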5.3.2 Safety urinalysis

Urinalysis for pH blood, protein, urine beta-2-microglobulin and albumin/creatinine ratio will be done at screening and visits 1, 2, 4, 5 and 6 and urine for cystatin-c will be collected at visits 1, 4, 5 & 6. A urine pregnancy test will be completed on females only, at all trial visits. Frequency of abnormal urine PH blood and protein per patient over time and positive pregnancy tests will be enumerated.

In addition to the final report, interim safety reports will be circulated to DSMB for review after the sentinel patient and the 4th patient receiving his/her first injection.

5.3.3 Gold concentration

At visits 1, 1b, 3b, 4, 5 and 6 blood and urine samples will be taken for gold concentrations to enable assessment of gold excretion. Laboratory measurements for these will be performed at the LGC laboratory, Cambridgeshire. Concentration of gold for each patient over time will be analysed by half-life of elimination at the end of the study.

The major organ of accumulation and excretion of the gold nanoparticles is the kidney. Safety reports on markers of kidney function in blood (levels of electrolytes, urea, creatinine, calcium, phosphate, and magnesium) and urine (blood in urine, protein in urine, cystatin-c and beta-2-microglobulin) have already been covered in 5.3.1 and 5.3.2.

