**Table 1: Schedule of study visits**

Visit number	Screening		Pre V1	Treatment							Follow up				Optional	
	-2	-1		1	1b	1C	2	3	3b	3C	4	Pre V5	5	6	7	any time post dosing
Weeks	These visits can be combined. Treatment must start within 3 months of screening commencing 		A minimum of 72 hours prior to visit 1	0	1 day post visit1	3 to 5 days post visit 1	4	8	1 day post visit3	3 to 5 days post visit 3	9	A minimum of 72 hours prior to visit 5	14	20	52	
Days				0			28	56			63 (or one week post final injection)		98	140 (85 days post final dose)	366 (311 days post. final dose +/- 14 days)	
Informed consent	X															
Study drug administration				X			X	X								
Follow up telephone call 24 hours post IMP				X			X	X								
Physical Exam & ECG	X			X			X	X					X		X	
 Serum for AABs and immune markers				X							X		X		X	
DRB1*0401 genotype	X															
MMTT				X									X		X	
Photographs at injection site				X			X	X			X		X	X	X	
Blood sample to accompany skin studies (optional)								X								
Stitch removal from biopsy site (optional)										X						
urine or random serum c-peptide post meal		X		X									X		X	
72 hour continuous glucose monitoring			Attach CGM	X								Attach CGM	X		X	
Serum for Cystatin C				X							X		X	X	X	
Urinalysis for blood, protein, and beta-2 microglobulin		X		X			X				X		X	X	X	
Serum and urine (morning) sample to measure gold concentrations				X pre dose	X 				X 		X		X	X	X	
T cell (immune biomarker) assays (blood)				X				-			X		X		X	
 LN aspiration 0/3-5d				X		X		X		X						
 Safety blood samples		X		X			X				X		X	X	X	
HbA1c measurement		X		X			X				X		X		X	
Vital signs	X	X		X			X	X			X		X	X	X	
Adverse Event assessment/con meds		X	X	X	X	X	X	X	X	X	X	X	X	X	X	
Urine pregnancy test		X		X			X	X					X	X		
Record of insulin use	X			X			X	X					X		X	
 Blood glucose profile/insulin usage				X			X	X					X	X	X	

Assessment of glycaemic control/review blood sugar recordings				X				X	X					X		X	
Skin biopsy (optional) 																	X
Contact hypersensitivity testing (optional) 																	X
Suction blister (optional) 																	X
XHFS survey				X										X			
ADDQoL				X										X		X	
DTSQs				X										X		X	
DTSQc														X			

Screening can be up to 3 months

Treatment visits 1, 2 and 3 should be every 28 days +/- 3 days and follow up visit 5 should be at 14 weeks +/- 1 week

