## 10 PHARMACOVIGILANCE

### 10.1 Specification, timing and recording of safety parameters

The major associated safety parameters are evidence of induction of hypersensitivity and exacerbation of  $\beta$ -cell specific autoimmunity with accelerated  $\beta$ -cell loss. To address general safety concerns at screening and 0, 4, 8 and 14 weeks a physical examination will be conducted. A review of AEs will be performed at all visits and blood will be drawn at screening, weeks 4, 9, 14 & 20 to examine the full blood count; urea, electrolytes and creatinine; liver function tests; (prothrombin time, total bilirubin, total protein, albumin, AST (SGOT), SGPT (ALT), alkaline phosphatase; thyroid stimulating hormone; immunoglobulins (G, A, M); calcium; magnesium, phosphate, lipid profile (total cholesterol, LDL, HDL, triglyceride). Urinalysis for pH blood, protein, urine beta-2-microglobulin and albumin/creatinine ratio will be done at screening and visits 1, 2, 4, 5 and 6 and urine for cystatin-c will be collected at visits 1, 4, 5 & 6. A urine pregnancy test will be completed on females only, at all trial visits. At visits 1, 1b, 3b, 4, 5 and 6 blood and urine samples will be taken for gold concentrations to enable assessment of gold excretion. Laboratory measurements for these will be performed at the Midatech Pharma laboratory, Spain.

The safety of the investigational medicinal product (IMP) C19-A3 GNP has been extensively studied in pre-clinical toxicity studies. No signs of toxicity and no significant adverse effects in the organs and the >40 tissues examined were seen, not even at doses that were up to 500-fold higher than the intended dose in this clinical study, and given daily during 14 consecutive days. The studies revealed that the major organ of accumulation and excretion of the gold nanoparticles is the kidney, and to a much lesser extent the liver and spleen. Significant quantities of gold were only detectable in kidneys, which collected on average 30 % of the total dose administered (in rats) over the 14 day period, with a half-life of elimination of circa

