2.1. Trial design

The study is a two centre, open-label, uncontrolled single group phase 1A study of C19-A3 GNP peptide (10 µg peptide equivalent content) administered via Nanopass microneedles every 28 days for 8 weeks (3 doses), with follow-up for 12 weeks (20 weeks in total from first dose). Treatment will be given into the arm at a volume of 50ul. A schedule of study visits and procedures carried out at each study visit are shown in table 1.

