4.2. Protocol deviations

Patients will be allowed to attend for follow up visit 4 (week 9) +/- 1 day of schedule, visit 5 (week 14), +/- 1 week of visit schedule and visit 6 (week 20) must be a minimum of 85 days post final dose/+2 weeks. Any visits outside of this guidance will be considered a protocol deviation.

All protocol violations and deviations as well as number of patients involved will be enumerated at the end of the study. A patient will be defined as being compliant with the protocol if s/he has taken all the three injections on target (within window) dates. Adherence to intervention will be enumerated according to treatment/followup on target (within window), protocol violations/deviations and missed dose/followup across the study schedule as set out in dummy table (ii) in Appendix 1.

Data from all enrolled patient will be included in analysis of safety as specified in section 5.1.1. and 5.3. Metabolic and immunological outcomes of patients who have missed or delayed dose/followup will also be explored with analysis specified in section 5.1.2

5. Analysis strategy

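### SAP 5.3.3 does not say which gold samples or model give the half-life, and SAP 5.2 imputes missing values with no exemption for gold; either gap can lengthen the estimate materially

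*SAP*

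**What the plan says.** On sampling, SAP 5.3.3 states: "At visits 1, 1b, 3b, 4, 5 and 6 blood and urine samples will be taken for gold concentrations". On analysis it states only: "Concentration of gold for each patient over time will be analysed by half-life of elimination at the end of the study".

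The dosing in SAP 2.1 is "administered via Nanopass microneedles every 28 days for 8 weeks (3 doses), with follow-up for 12 weeks (20 weeks in total from first dose". Protocol Table 1 marks the visit 1 gold sample as taken before the dose. It places visit 1b at "1 day post visit1" and visit 3b at "1 day post visit3". SAP 4.2 fixes the windows of the next two visits: "follow up visit 4 (week 9) +/- 1 day of schedule, visit 5 (week 14), +/- 1 week of visit schedule". For the last scheduled visit, nominally at 20 weeks, it requires at least 85 days since the third injection and allows two weeks beyond that.

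SAP 5.2 applies to any missing data. It names three imputations (worst case, last observation carried forward, and the mean of the non-missing cases) and a sensitivity analysis across those three data sets and the complete cases. Gold is not excepted.

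The only half-life in either document is about 17 days, in Protocol 10.1, for gold in the kidneys of rats ("with a half-life of elimination of circa"). Neither document gives a human value for serum or urine.

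**The concern.** A half-life is the output of a model, so the choice of samples and the treatment of dose times are the method. In the listed series, visit 1 precedes any drug, visit 1b follows one dose, and visits 3b to 6 follow three. No gold sample falls between day 1 and day 57. A single decline drawn from day 1 to day 140 treats the gold added by doses 2 and 3 as gold that was never cleared, which flattens the slope and lengthens the half-life.

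The imputation rule is a second route to the same error. Carrying a concentration forward asserts that nothing was eliminated between two visits, which is the opposite of what a half-life measures.

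This is a first-in-man study. SAP 5.3.3 names the kidney as the major organ of gold accumulation and excretion, and half-life is the only analysis of gold that the SAP specifies. With about eight patients, one or two distorted values would show in any summary.

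**Working it through.** **Inputs.** Doses at days 0, 28 and 56 (SAP 2.1). Post-dose gold samples at nominal days 1, 57, 63, 98 and 140 (visits 1b, 3b, 4, 5, 6). Illustrative true half-life 17 days (Protocol 10.1, rat kidney). Assumptions that are not in the documents: equal doses, one compartment, instant absorption, ordinary least squares on log concentration. The visit 1 sample is pre-dose, so it carries no drug gold and cannot enter a log fit. The documents give no data behind the 17 days, so there is no plan figure to reproduce.

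**Step 1: concentrations.** With k = ln 2 / 17 = 0.04077 per day, C(t) is the sum of exp(−k(t − d)) over doses d already given. At day 57 this is 0.098 + 0.307 + 0.960 = 1.364.

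| Day | 1 | 57 | 63 | 98 | 140 |
|---|---|---|---|---|---|
| C | 0.960 | 1.364 | 1.068 | 0.256 | 0.046 |
| ln C | −0.041 | 0.311 | 0.066 | −1.361 | −3.073 |

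**Step 2: one line through all five visits.** Mean day 71.8; Sxx = 10,646.8; Sxy = −247.56. Slope = −247.56 / 10,646.8 = −0.02325. Half-life = 0.6931 / 0.02325 = **29.8 days**, and 29.8 / 17 = 1.75, an excess of 75%.

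**Step 3: visits 3b to 6 only.** Mean day 89.5; Sxx = 4,381; Sxy = −178.63. Slope = −0.04077; half-life **17.0 days**. A model of all post-dose samples that includes the three dose times also returns 17.0.

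**Step 4: how far the all-visit result depends on the inputs.**

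| True half-life (days) | All-visit fit (days) | Excess |
|---|---|---|
| 5 | 7.98 | 60% |
| 10 | 16.3 | 63% |
| 17 | 29.8 | 75% |
| 30 | 65.4 | 118% |

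With a true 17 days and visits at the edges of their windows, the fit ranges from 25.6 to 31.4 days (+51% to +85%). With 20% lognormal error, the all-visit fit has a median of 29.8 (5th to 95th percentile 26.3 to 34.6), against 17.0 (15.2 to 19.4) for visits 3b to 6.

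**Step 5: visit 6 missing, visit 5 carried forward.** Use the visits 3b to 6 fit, with the day-98 value entered again at day 140.

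- The deviations of the days from 89.5 are −32.5, −26.5, 8.5 and 50.5.
- After the last dose ln C falls by k per day, so the slope is −k × (−32.5×57 − 26.5×63 + 8.5×98 + 50.5×98) / 4,381 = −k × 2,260 / 4,381.
- The half-life is multiplied by 4,381 / 2,260 = 1.94, whatever its true value. At 17 days this gives **33.0 days**.
- The same substitution in the all-visit fit gives 56.4 days.
- Complete cases (days 57, 63, 98) return 17.0.

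**Step 6: slow release from the skin.** Protocol 6.14 says that the gold mark may still be visible 3 months or more after injection. With elimination held at 17 days and assumed absorption half-lives of 5, 10 and 30 days, the visits 3b to 6 fit gives 22.9, 29.2 and 87.5 days. The all-visit fit gives 122 days in the first case and a negative half-life in the other two.

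**The case against.** The strongest reply is that the SAP does not order an all-visit fit. Visits 3b, 4, 5 and 6 already supply four samples after the last dose, and in the worked example the concentration rises from day 1 to day 57, so a careful analyst would see that one decline does not describe the series. This stands. A reader might infer that the plan inflates the half-life by 75%. The documents do not support that: the text permits such a fit but does not prescribe it, and 75% rests on a rat kidney figure applied to human serum or urine.

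It is also fair that restricting the samples recovers the true value only under rapid absorption. Step 6 shows that it need not do so if the skin acts as a depot. The restriction is better than the all-visit fit, but it is not shown to be unbiased.

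On imputation, SAP 5.2 includes the complete-case data set, so carried-forward values are not the only result. That softens the point. It does not settle which half-life is reported.

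Three further inferences should be resisted:

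- **Visit 7.** Leaving it out of 5.3.3 is not a defect. The visit is optional, and the visit list in Protocol 10.1 matches the SAP's. At 17 days, day 366 is (366 − 57) / 17 = 18.2 half-lives after day 57, or about 0.0003% of that level.
- **Redosing.** Neither document describes redosing plans based on this half-life.
- **Importance.** Gold half-life is not listed as a primary or secondary endpoint, and renal safety is followed directly through blood and urine markers. An overstated half-life would also err on the cautious side about accumulation.

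The documents give no assay limit, so how often values would fall below it is unknown. At 17 days the day-140 level is 0.046 / 1.364, about 3% of day 57, so it is possible.

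**Conclusion.** The concern holds as an unspecified method combined with an unsuitable imputation rule. It is not a demonstrated bias in the planned result. If all five post-dose visits were fitted as one log-linear decline, the half-life would be too long: 29.8 days for a true 17, and about 60% to 118% too long for true values of 5 to 30 days, given one compartment, equal doses and rapid absorption. If last observation carried forward filled a missing visit 6, even the post-final-dose fit would be 1.94 times too long, 33 days for 17. The direction of both errors comes from the dose and visit schedule and does not depend on the rat figure; the sizes are illustrative. Because this is a supporting safety measure and the remedy is wording, the change is worth making before database lock, but it does not threaten the primary analysis.

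**What to change.** In SAP 5.3.3:

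1. Estimate each patient's half-life from samples after the final dose only (visits 3b, 4, 5 and 6), using actual sampling times. Alternatively, fit all post-dose samples with a model that includes the actual dose times.
2. State that gold concentrations are exempt from the imputation in SAP 5.2, and treat values below the assay limit as censored.
3. Report the result as an apparent terminal half-life, and note that slow release from the skin can lengthen it.

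No new samples or visits are needed. The cost is a SAP amendment, and some patients may have no estimate where too few values can be quantified.
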